6.5.1 DE Subjects

DE phase subjects will attend the unit as outpatients for the End of Dosing (Cycle 1 Day 29 ± 2) or the Early Discharge visit. A full physical examination will be performed and evaluation of EDSS, weight, vital signs, safety blood and urine samples, pregnancy testing if applicable, ECG, adverse events and concomitant medications will be completed.

A cranial MRI will be performed at the End of Dosing.

6.5.2 DC Subjects

DC phase subjects will attend the unit as outpatients for the End of Dosing (Cycle 3 Day 29 ± 2) or the Early Discharge visit. A full physical examination will be performed and evaluation of weight, vital signs, safety blood and urine samples, pregnancy testing if applicable, ECG, MSFC, FSS, FS-36, EDSS, adverse events and concomitant medications will be completed.

A cranial MRI will be performed at the End of Dosing.

Version 5

6.6 Follow-up (15 Days Post-End of Dosing) – All Subjects

All DE and DC phase subjects will attend the unit as outpatients for the Follow-up visit. A full physical examination will be performed and evaluation of weight, vital signs, safety blood and urine samples, pregnancy testing if applicable, ECG, adverse events and concomitant medications will be made.

Version 5

Table 2 Schedule of Events (DE Phase)

| | | | | | | | Clini | c Visit | | | | | | | | | |
|--|-------------------------|------------------|---|---------------------|---|----------------------|-------|----------------------|--|----------------|----------------|--|--|--|--|--|--|
| | | | | | | ay | 10 | 22 | End of Dosing or Early Discharge: (15 ± 2 Days All Subjects Post-End of 22 23 Day 29 Dosing): All | | | | | | | | |
| Study Procedures | Pre-Study (-28 days) | 1 Baseline | 2 | 8 + 1 day | 9 | 15 + 1 day | 16 | 22 + 1 day | 23 | ± 2 days | Subjects | | | | | | |
| Medical history | X | | | | | | | | | - | • | | | | | | |
| Physical examination | X ¹ | X ^{2,3} | | X ² | | X ² | | X ² | | X ¹ | X ² | | | | | | |
| Neurological examination ⁴ | х | X ³ | | | | | | | | х | | | | | | | |
| Inclusion/exclusion | х | | | | | | | | | | | | | | | | |
| criteria | ^ | | | | | | | | | | | | | | | | |
| Informed consent | Х | | | | | | | | | | | | | | | | |
| Body weight | Х | X ³ | | | | | | Х | | Х | Х | | | | | | |
| Vital signs ⁵ | Х | Х | | Х | | Х | | Х | | Х | Х | | | | | | |
| Clinical laboratory testing ⁶ | Х | X ³ | | x | | х | | х | | x | х | | | | | | |

¹ Thorough examination pre-study and at end of study dosing.

² Symptom-directed examination weekly and at follow-up.

³ If pre-study assessment was performed within 3 days prior to baseline, assessments do not need to be repeated prior to initiation of dosing.

⁴ Neurological examination will be conducted at screening, baseline and end of dosing, and at other timepoints when indicated by history and adverse events.

⁵ Temperature, pulse, respiration, blood pressure pre-study; prior to dosing, midway through (5 minutes), and 15 and 30 minutes, 2 and 4 hours post-dosing (and 6, 8, 10, 12, 16, 20 and 24 hours post-dose on Day 1) at each clinic visit, and at follow-up.

⁶ Hematology (red blood cell [RBC] count, hemoglobin, hematocrit, mean corpuscular volume [MCV], mean cell haemoglobin concentration (MCHC), platelet count, white blood cell [WBC] count, differential cell count [absolute and percentage; neutrophils, lymphocytes, monocytes, eosinophils, basophils], and reticulocyte count [absolute and percentage], coagulation (prothrombin time [PT], partial thromboplastin time [PTT], INR), serum chemistry (conjugated bilirubin, alanine aminotransferase [ALT], aspartate aminotransferase [AST], alkaline phosphatase, lactate dehydrogenase [LDH], gamma-glutamyltransferase, amylase, lipase, total protein, albumin, globulin, sodium, potassium, chloride, bicarbonate, calcium, adjusted calcium, phosphate, magnesium, glucose, urea,

Version 5

| | | | Clinic Visit | | | | | | | | | |
|-----------------------------|------------|-----------------|-----------------|-----------------|-----------------|--|---|-----------------|-----------------|----------|--------------|--|
| | | | | | | End of Dosing or Early Discharge: All Subjects | Follow-Up (15 + 2 Days Post-End of | | | | | |
| | Pre-Study | 1 | 2 | 8 | 9 | 15 | 16 | 22 | 23 | Day 29 | Dosing): All | |
| Study Procedures | (-28 days) | Baseline | | + 1 day | | + 1 day | | + 1 day | | ± 2 days | Subjects | |
| ECG ⁷ | Х | Х | | Х | | Х | | Х | | Х | Х | |
| Pregnancy test ⁸ | Х | Х | | | | | | Х | | Х | Х | |
| EDSS ⁹ | Х | Х | | | | | | | | Х | | |
| Cranial MRI | Х | | | | | | | | | Х | | |
| Concomitant | х | х | | х | | х | | х | х | х | Х | |
| medications | ~ | ^ | | ~ | | | | | Λ | | | |
| Adverse events | | Х | | Х | | Х | | Х | | Х | Х | |
| Study Drug | | х | | x | | x | | х | | | | |
| Administration | | ~ | | ^ | | ^ | | ^ | | | | |
| PD & Immune | | | | | | | | 10 | | | | |
| parameter sampling | | X ¹⁰ | | X ¹⁰ | | X ¹⁰ | | X ¹⁰ | | | | |
| Pre-each dose | | | | | | | | | | | | |
| PD & Immune | | | | | | | | | | | | |
| parameter sampling | | | X ¹¹ | | X ¹¹ | | X ¹¹ | | X ¹¹ | | | |
| 24hrs Post-each | | | ^ | | ~ | | ~ | | ~ | | | |
| dose | | | | | | | | | | | | |

creatinine, follicle stimulating hormone [FSH; at pre-study for postmenopausal women only]), and urinalysis (pH, specific gravity, protein, glucose, ketones, white blood cells, red blood cells, leucocyte esterase, urobilinogen, bilirubin, culture where applicable) pre-study, prior to the first dose, weekly, at End of Dosing, and at Follow-Up. Serology for Hepatitis B, C and HIV and urine drug of abuse at screening only.

⁷ Performed pre-study, pre-dose and 30 minutes, 1, 2, 4 hours (and 6, 8, 12 and 24 hours on Day 1) post-dose, at end of study dosing, and at follow-up.

⁸ Screening (serum); otherwise, urine dipstix, confirmed with serum hCG if equivocal.

⁹ EDSS will be assessed at Screening, Baseline, End of Dosing and at other timepoints when clinically indicated by neurological examination

¹⁰ 3 x 10 mL whole blood sample collected pre-each dose

¹¹ 3 x 10 mL whole blood sample collected 24 hours post each dose

Version 5

| | Pre- | Clinic Visit (Cycle 1) | | | | | | | | | |
|--|----------------|------------------------|-----|----------------|---|----------------|----|----------------|----|------------------|--|
| | Study | | Day | | | | | | | | |
| | (-28 | 1 | 2 | 8 | 9 | 15 | 16 | 22 | 23 | Early Discharge: | |
| Study Procedures | days) | Baseline | | + 1 day | | + 1 day | | + 1 day | | All Subjects | |
| Medical history | Х | | | | | | | | | | |
| Physical examination | X ¹ | X ^{2,3} | | X ² | | X ² | | X ² | | X ¹ | |
| Neurological examination ⁴ | x | X ³ | | | | | | | | x | |
| Ophthalmologic examination ⁵ | x | | | | | | | | | x | |
| Inclusion/ exclusion criteria | х | | | | | | | | | | |
| Informed consent | Х | | | | | | | | | | |
| Body weight | Х | X ³ | | | | | | Х | | Х | |
| Vital signs ⁶ | Х | Х | | Х | | Х | | Х | | X | |
| Clinical laboratory testing ⁷ | x | X ³ | | х | | х | | х | | х | |

Table 3 Schedule of Events (DC Phase – Cycle 1)

¹ Thorough examination pre-study and at end of study dosing.

² Symptom-directed examination weekly during the first cycle, once each subsequent cycle, and at follow-up.

³ If pre-study assessment was performed within 3 days prior to baseline, assessments do not need to be repeated prior to initiation of dosing.

⁴ Neurological examination will be conducted at screening, baseline and end of dosing, and at other timepoints when indicated by history and adverse events.

⁵ Visual acuity determination, biomicroscopy, and dilated fundoscopy during screening and within a week of the Early Discharge.

⁶ Temperature, pulse, respiration, blood pressure pre-study; prior to dosing, midway through (5 minutes), and 15 and 30 minutes, 2 and 4 hours (and 6, 8, 10, 12, 16, 20 and 24 hours post-dose on Day 1) post-dosing at each clinic visit, and at follow-up.

⁷ Hematology (red blood cell [RBC] count, hemoglobin, hematocrit, mean corpuscular volume [MCV], mean cell haemoglobin concentration [MCHC], platelet count, white blood cell [WBC] count, differential cell count [absolute and percentage; neutrophils, lymphocytes, monocytes, eosinophils, basophils], and reticulocyte count [absolute and percentage], coagulation (prothrombin time [PT], partial thromboplastin time [PTT], INR), serum chemistry (conjugated bilirubin, alanine aminotransferase [ALT], aspartate aminotransferase [AST], alkaline phosphatase, lactate dehydrogenase [LDH], gamma-glutamyltransferase (GGT), amylase, lipase, total protein, albumin, globulin, sodium, potassium, chloride, bicarbonate, calcium, adjusted calcium, magnesium, phosphate, glucose, urea, creatinine, , follicle stimulating hormone [FSH; at pre-study for postmenopausal women only]), and

Version 5

| | Pre- | | | Clinic Visit (Cycle 1) | | | | | | |
|-----------------------------|-------|-----------------|-----------------|------------------------|-----------------|----------------|-----------------|----------------|-----------------|------------------|
| | Study | | Day | | | | | | | |
| | (-28 | 1 | 2 | 8 | 9 | 15 | 16 | 22 | 23 | Early Discharge: |
| Study Procedures | days) | Baseline | | + 1 day | | + 1 day | | + 1 day | | All Subjects |
| ECG ⁸ | Х | Х | | Х | | Х | | Х | | Х |
| Echocardiogram | Х | | | | | | | | | |
| Pregnancy test ⁹ | Х | | | | | | | Х | | Х |
| EDSS ¹⁰ | Х | Х | | | | | | | | Х |
| MSFC | | Х | | | | | | | | Х |
| FSS | | Х | | | | | | | | Х |
| SF-36 | | Х | | | | | | | | Х |
| Cranial MRI | Х | | | | | | | | | Х |
| Concomitant | х | х | | х | | х | | х | х | х |
| medications | ^ | ^ | | ^ | | ^ | | ^ | ^ | ^ |
| Adverse events | | Х | | Х | | Х | | Х | | Х |
| Study Drug | | x | | x | | x | | x | | |
| Administration | | ~ | | ~ | | ^ | | ^ | | |
| PD & Immune | | | | | | | | | | |
| parameter sampling | | X ¹¹ | | X ⁹ | | X ⁹ | | X ⁹ | | |
| Pre-each dose | | | | | | | | | | |
| PD & Immune | | | | | | | | | | |
| parameter sampling | | | X ¹² | | X ¹⁰ | | X ¹⁰ | | X ¹⁰ | |
| 24hrs Post-each dose | | | | | | | | | | |

urinalysis (pH, specific gravity, protein, glucose, ketones, white blood cells, red blood cells, leucocyte esterase, urobilinogen, bilirubin, culture where applicable) pre-study, prior to the first dose, weekly during Cycle 1, at End of Dosing, and at Follow-Up (all subjects). For DC phase subjects only, Days 8 and 22 during Cycles 2 and 3 and at the end of Cycles 4 and 6. Serology for Hepatitis B, C and HIV and urine drug of abuse at screening only.

⁸ Performed pre-study, pre-dose and 30 minutes, 1, 2, 4 hours (and 6, 8, 12 and 24 hours on Day 1) post-dose, at end of study dosing, and at follow-up.

⁹ Screening (serum); otherwise, urine dipstix, confirmed with serum hCG if equivocal.

¹⁰ EDSS will be assessed at Screening, Baseline, Early Discharge and at other timepoints when clinically indicated by neurological examination

¹¹ 3 x 10 mL whole blood sample collected pre-each dose

¹² 3 x 10 mL whole blood sample collected 24 hours post each dose

Version 5

Table 4 Schedule of Events (DC Phase – Cycles 2-3)

| | Clinic Visit (Cycles 2-3) | | | | | | | | | |
|---|---------------------------|--------------|----------------------|----------------------|--|--|--|--|--|--|
| | | Days (ea | ch cycle) | | | | | | | |
| Study Procedures | 1 + 1 day | 8 + 1 day | 15 + 1 day | 22 + 1 day | End of Study Dosing or Early Discharge: All Subjects | Follow-Up (15 +2 Days Post-End of Dosing): All Subjects | | | | |
| Physical examination | X ¹³ | | | | X ¹ | Х | | | | |
| Neurological examination ¹⁴ | Х | | | | Х | | | | | |
| Ophthalmologic examination ¹⁵ | | | | | х | | | | | |
| Body weight | | | | | Х | Х | | | | |
| Vital signs ¹⁶ | Х | Х | Х | Х | Х | Х | | | | |
| Clinical laboratory testing ¹⁷ | | Х | | Х | Х | Х | | | | |
| ECG ¹⁸ | х | х | х | х | х | Х | | | | |
| Pregnancy test ¹⁹ | | | | Х | Х | Х | | | | |

¹³ Symptom-directed examination once each cycle and at follow-up.

¹⁵ Visual acuity determination, biomicroscopy, and dilated fundoscopy within a week of End of Dosing or Early Discharge.

¹⁶ Temperature, pulse, respiration, blood pressure pre-study; prior to, midway through, and 15 and 30 minutes, 2 and 4 hours post-dosing at each clinic visit, and at follow-up.

¹⁷ Hematology (red blood cell [RBC] count, hemoglobin, hematocrit, mean corpuscular volume [MCV], mean cell haemoglobin concentration [MCHC], platelet count, white blood cell [WBC] count, differential cell count [absolute and percentage; neutrophils, lymphocytes, monocytes, eosinophils, basophils,], and reticulocyte count [absolute and percentage], coagulation (prothrombin time [PT], partial thromboplastin time [PTT], INR), serum chemistry (conjugated bilirubin, alanine aminotransferase [ALT], aspartate aminotransferase [AST], alkaline phosphatase, lactate dehydrogenase [LDH], gamma-glutamyltransferase (GGT), amylase, lipase, total protein, albumin, globulin, sodium, potassium, chloride, bicarbonate, calcium, adjusted calciumphosphate calcium, magnesium, glucose, urea, creatinine, follicle stimulating hormone [FSH; at pre-study for postmenopausal women only]), and urinalysis (pH, specific gravity, protein, glucose, ketones, white blood cells, red blood cells, leucocyte esterase, urobilinogen, bilirubin).

50

¹⁴ Neurological examination will be conducted on Day 1 of each cycle, at End of Study Dosing or Early Discharge and at other timepoints as indicated by history and adverse events.

Version 5

| | Clinic Visit (Cycles 2-3) | | | | | | | | |
|-----------------------------------|---------------------------|--------------|----------------------|----------------------|--|--|--|--|--|
| | | Days (ea | ch cycle) | | | | | | |
| Study Procedures | 1 + 1 day | 8 + 1 day | 15 + 1 day | 22 + 1 day | End of Study Dosing or Early Discharge: All Subjects | Follow-Up (15 +2 Days Post-End of Dosing): All Subjects | | | |
| EDSS ²⁰ | Х | | | | Х | | | | |
| MSFC ⁸ | Х | | | | Х | | | | |
| FSS ⁸ | Х | | | | Х | | | | |
| SF-36 | | | | | Х | | | | |
| Cranial MRI | | | | | х | | | | |
| Concomitant medications | Х | Х | Х | Х | Х | | | | |
| Adverse events | Х | Х | Х | Х | Х | | | | |
| Study Drug Administration | Х | Х | Х | Х | | | | | |
| PD & Immune parameter sampling | | | | X ²¹ | | | | | |

¹⁹ Screening (serum); otherwise, urine dipstix, confirmed with serum hCG if equivocal.

²⁰ Expanded Disability Status Scale (EDSS), MS Functional Composite (MSFC), and Fatigue Severity Scale` (FSS) performed on Day 1 of each cycle and at end of study dosing and at other timepoints where indicated by neurological examination. ²¹ 3 x 10 mL whole blood sample collected pre-dose on Day 22 of each cycle.

7. Safety Assessments

The primary endpoint is to determine the safety profile and MTD of MIS416. Assessments will include characterization of DLTs; characterization of the type, incidence, severity, timing, seriousness and relationship to treatment of AEs; effects on vital signs and laboratory parameters; changes in ECGs and ophthalmologic examinations.

7.1 Adverse events

The definition of an adverse event is given in section 10.2.

Adverse events will be monitored throughout the study and recorded on the AE page of the CRF. Adverse events will be graded according to the Toxicity Grading Scale for Healthy Adult and Adolescent Volunteers Enrolled in Preventive Vaccine Clinical Trials (Guidance for Industry) issued by US DHHS September 2007 and modified to include a systemic line item for rigors/chills. The relationship of adverse event to study drug will be determined by the investigator and details of this classification is given in section 8.

7.2 History and Physical and Neurological Examinations

At screening, all subjects will undergo a medical history and physical examination. A focused physical examination will be repeated weekly during the first cycle, once each subsequent cycle, at end of dosing or early discharge and at follow up (15 days post end of dosing). A neurological examination will be performed at screening, at Day 1 of each cycle, and at end of dosing or early discontinuation.

Unscheduled physical and neurological assessments will be conducted at other timepoints when clinically indicated by history and adverse events.

7.3 Ophthalmologic Examinations

In the DC phase only, subjects will undergo visual acuity determination, biomicroscopy, and dilated fundoscopic examination at screening and within a week of the End of Study or Early Withdrawal visit.

7.4 Safety Laboratory Tests

Blood and urine samples will be taken for safety laboratory assessment (haematology, biochemistry, serology and urinalysis) as described in Tables 2, 3 and 4. The tests will be performed at a local laboratory according to their laboratory standard operating procedures. The normal ranges will be supplied to the investigator and sponsor prior to the start of the study. The following tests will be included in each panel:

Version 5

- Haematology: Red blood cells, haemoglobin, haematocrit, mean cell volume, mean cell haemoglobin, mean cell haemoglobin concentration, platelet count, white blood cell count, reticulocytes (absolute and percentage), differential (absolute and percentage): neutrophils, lymphocytes, monocytes, eosinophils, basophils.
- Coagulation: Prothrombin Time (PT), Activated Partial Thromboplastin time (APTT), INR
- Biochemistry: Sodium, potassium, calcium, glucose, albumin, globulin, adjusted calcium, phosphate, bicarbonate, chloride, magnesium, aspartate aminotransferase, alanine aminotransferase, alkaline phosphatase, glutamyl transferase, lactate gammadehydrogenase, conjugated bilirubin, total protein, plasma creatinine, urea, amylase, lipase, follicle stimulating hormone (screening only where applicable), quantitative hCG (where applicable), Urinalysis: Protein, glucose, pH, leucocyte esterase, white blood cells, red blood cells, ketones, urobilinogen, , specific gravity, bilirubin, culture (if applicable), qualitative hCG (where applicable)

Urine drug of abuse screen: Opiates, amphetamines, cannabinoids, benzodiazepines, methadone

Serology: Hepatitis B, hepatitis C, HIV

A total of up to approximately 343 mL of blood is required during the DE phase and approximately 506 mL of blood is required during the DC phase with both quantities including PD and immune parameter sampling, per Section 7.7.

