In mid and high dose groups there were findings of grade 1 and grade 2 desirable effects, consistent with the test items mode of action, comprising histiocytic proliferation in liver, lung, and spleen, oval cell proliferation, and bone marrow hypercellularity. Adverse findings, in particular in the high dose group, included treatment related adverse hematology and chemistry, organs weights, gross pathology and histopathology including erythrophagoctosis in liver and spleen, increased hemosiderosis (greater than grade 1) in spleen, lymphoid depletion in spleen, endothelial hyperplasia in lungs and eyes, and glomerular hypercellularity in kidneys.

Version 5

In view of the results NOAEL for MIS416 when administered twice weekly for 4 weeks to New Zealand white rabbits by i.v. route is greater than 50 μ g/kg and less than 500 μ g/kg bodyweight under the test conditions and doses employed.

1.4.4 26 Week Repeat Dose Study

In this GLP repeat dose toxicity study, respective groups of 6 animals per sex per group were administered MIS416 intravenously once weekly for 26 weeks with doses of 0 ug (control), 20 ug, 200 ug or 1000 ug /kg. Following the treatment period, 2 animals per group were held for a 4 week recovery period.

At the lowest dose of 20 μ g/kg there were no deaths. Principal effects included minimal leukocyte infiltration into the choroid of the eye, minimal portal inflammation in the liver, with no effects on liver enzymes, minimal mixed leukocyte infiltration in the lung in 2/8 animals, and lymphoid hyperplasia of the spleen in one of eight animals. Absolute and relative spleen weights were increased as well.

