At the middle dose (200 μ g/kg) there was no mortality whereas at the high (1000 μ g/kg) dose three animals died or were sacrificed when observed to be in a moribund condition during the fourth and fifth month. Cause of death was attributed to cardiac myofibre degeneration and necrosis. This finding, or any cardiac findings, was not found in any other surviving animal at any dose. Additional effects seen at these doses included small but statistically significant reductions in red cell parameters, slight decrease in platelet counts, increased globulin values with a corresponding decrease in Albumin/Globulin (A/G) ratio, and decreased calcium (females only). Although occasional random increases in liver enzyme levels were seen in some animals, there was no clear nor consistent effect. Histopathological evaluation of tissues showed effects in the spleen (hyperplasia of the germinal center and hyperplasia of the red pulp), liver (portal inflammation, with necrosis and fibrosis at the high dose only), lung (mixed leukocyte infiltration), eye (mixed leukocyte infiltration of the choroid), and kidney (tubular degeneration and regeneration, glomerulopathy and heterophil infiltration in high dose animals only).

In conclusion, the intravenous administration of MIS416 to rabbits on a weekly basis resulted in toxicological effects at the high dose that included mortality (3/8 animals), generally mild clinical pathology findings and histopathological effects in the eye, heart, kidney, liver, lung and spleen. These findings had either resolved or showed advancing resolution at the end of the four-week recovery period. Some of these findings, except mortality, were noted at the middle dose. Effects noted at the lowest dose of 20 ug/kg/dose were substantially reduced in incidence, and were limited to minimal leukocyte infiltration in the eye, minimal portal inflammation in the liver (no effects on liver enzymes) and lymphoid hyperplasia in the spleen in 1/8 animals. Thus, the dose of 20 ug/kg/dose is considered the NOAEL for the administration of MIS416 weekly for 26 weeks.

Version 5

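### All four chemistry lists schedule conjugated bilirubin as the only serum bilirubin; adding total bilirubin to the same samples would close a small gap in the safety data

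*Protocol*

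**What the plan says.** **Serum panel.** The biochemistry list in Section 7.4 contains "conjugated bilirubin, total protein, plasma creatinine, urea, amylase, lipase" and no other serum bilirubin. Table 2 footnote 6 (dose-escalation, DE), Table 3 footnote 7 (dose-confirmation, DC, Cycle 1) and Table 4 footnote 17 (DC Cycles 2–3) each open their chemistry list in the same way: "serum chemistry (conjugated bilirubin, alanine aminotransferase [ALT], aspartate aminotransferase [AST], alkaline phosphatase, lactate dehydrogenase [LDH".

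**Other relevant markers.** Section 7.4 also schedules ALT, AST, alkaline phosphatase, GGT, LDH, albumin, PT, INR, haemoglobin and haematocrit. Its haematology list includes "platelet count, white blood cell count, reticulocytes (absolute and percentage", and its urinalysis list includes "white blood cells, red blood cells, ketones, urobilinogen, , specific gravity, bilirubin, culture (if applicable".

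**Rabbit findings.** In the 4-week study (Section 1.4.3) the adverse findings at the mid and high doses, chiefly the high dose, included "erythrophagoctosis in liver and spleen, increased hemosiderosis (greater than grade 1) in spleen". In the 26-week study (Section 1.4.4) they included "liver (portal inflammation, with necrosis and fibrosis at the high dose only", together with small but significant falls in red-cell parameters. That section adds that liver enzyme rises were sporadic, without a clear or consistent effect.

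**Use of the data.** Section 7 makes laboratory effects part of the primary safety endpoint, and Section 4.4 allows a laboratory abnormality to be a dose-limiting toxicity (DLT). Section 14.5.3.3 plans changes from baseline and shift tables for each laboratory parameter except urinalysis.

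**The concern.** The animal work points to the liver and to red-cell turnover as places where the drug may act. Bilirubin bears on both, but the fractions differ: increased red-cell breakdown raises mainly the unconjugated fraction, and that is the fraction this panel leaves out. The protocol fixes the analyte list, so no later analysis can recover a quantity that was never assayed.

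What is at stake is the completeness of the laboratory part of the safety profile. A rise carried mainly by unconjugated bilirubin would leave the reported serum bilirubin unremarkable. A reviewer who wanted to look at transaminases and total bilirubin together, subject by subject, could not do so from the planned dataset.

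**Working it through.** The protocol states no figure here to reproduce. The check is a comparison of lists, a count of draws and one identity.

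**1. The four lists side by side**

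| Place | Conjugated | Total | Unconjugated |
|---|---|---|---|
| Section 7.4 | yes | no | no |
| Table 2, footnote 6 | yes | no | no |
| Table 3, footnote 7 | yes | no | no |
| Table 4, footnote 17 | yes | no | no |

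All four agree, so this is neither a slip in one table nor damage from text extraction.

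**2. What can be derived.** Total = conjugated + unconjugated. One measured term does not determine the other two.

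**3. Draws affected (maxima)**
- DE: screening, Days 1, 8, 15, 22 and 29, follow-up = 7.
- DC: screening and Days 1, 8, 15 and 22 of Cycle 1 (5), Days 8 and 22 of Cycles 2 and 3 (2 × 2 = 4), end of dosing (1), follow-up (1) = 11.
- Footnote 3 to Tables 2 and 3 lets a screening sample from within 3 days stand in for Day 1, so the actual count can be one lower.

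**4. Whether an ad hoc test would fill the gap**
- Section 12.2.7 calls for repeat testing after an unexplained, clinically relevant abnormal value. A mainly unconjugated rise need not produce an abnormal serum bilirubin to trigger it.
- Section 14.3.1.1 lists unscheduled results but keeps them out of tables by visit.
- Section 14.3.1.2 takes baseline from Day 1 or, failing that, screening. An ad hoc total bilirubin would have neither, and so no change from baseline and no shift.

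**5. Illustration (every input assumed; none is in the protocol).** Take total bilirubin 40 µmol/L, 10% conjugated, and upper limits of 20 (total) and 5 (conjugated). Reported conjugated = 0.10 × 40 = 4, below 5, while total is 40/20 = 2 times its limit. The result depends on the share: conjugated stays below its limit only while share < 5/total.

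| Total (µmol/L) | Share at which conjugated reaches 5 |
|---|---|
| 30 | 5/30 = 16.7% |
| 40 | 5/40 = 12.5% |
| 60 | 5/60 = 8.3% |

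**6. Dose context of the rabbit findings.** The top planned dose is 1000 µg (Section 11.1). At the 50 kg worst-case weight in Section 2.4 this is 1000/50 = 20 µg/kg. Per dose and per kg, without surface-area scaling:
- Necrosis and fibrosis arose at 1000 µg/kg weekly: 1000/20 = 50-fold higher.
- The 4-week high dose was 5000 µg/kg twice weekly: 5000/20 = 250-fold higher.
- The 26-week mid dose was 200 µg/kg: 200/20 = 10-fold higher.

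**The case against.** The strongest reply is that the panel is a legitimate choice with substantial cover. For red-cell destruction, the same draws measure red cell count, haemoglobin, haematocrit, reticulocytes, LDH and urine urobilinogen. For liver injury they measure ALT, AST, alkaline phosphatase, GGT, albumin, PT and INR, besides conjugated bilirubin. All the blood markers enter the shift tables. The rabbit lesions arose mainly at doses well above those planned, the red-cell falls were small, and the protocol does not report haemolysis. Nor does it rely anywhere on a joint transaminase–bilirubin rule; its liver eligibility limits use AST and ALT alone.

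Most of this stands, and it rules out three stronger inferences:

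- **That toxicity cannot be graded, or DLTs will be missed.** The laboratory grading rows are in the companion Operations Manual, which is not shown; Appendix 3 reproduces only rigors/chills and fever. Which bilirubin fraction the scale grades cannot be read from the protocol.
- **That total bilirubin is unobtainable.** Nothing bars an unscheduled test. It is the planned dataset that lacks it.
- **That such an event would leave every laboratory value normal.** Only the serum bilirubin result would be silent; other markers might well move.

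The reply does not remove the gap. Section 1.4.4 reports necrosis and fibrosis without a consistent enzyme signal, and minimal portal inflammation at the low dose without enzyme effects. Bilirubin might not have tracked those lesions either, but where enzymes were uninformative a second serum measure is reasonable.

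**Conclusion.** The point holds as a minor one. In 4 of 4 lists conjugated bilirubin is the only serum bilirubin. Total and unconjugated bilirubin therefore cannot be derived, given a baseline or tabulated at any of the up to 7 DE or 11 DC draws. The protocol does not contradict itself here, and neither the DLT rule nor the primary endpoint is shown to fail. What is lost is one complementary serum measure for two organ systems in which the protocol's own toxicology reports findings, with only partial cover from the other markers.

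The conclusion rests on reading the four lists as complete and on the general physiology that red-cell breakdown raises chiefly the unconjugated fraction. It does not rest on the numerical illustration, which uses assumed values and changes with the conjugated share.

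**What to change.** - In Section 7.4 and in the chemistry footnotes to Tables 2, 3 and 4, replace conjugated bilirubin with total and conjugated bilirubin, both run on the same sample.
- Include total bilirubin in the changes from baseline and shift tables of Section 14.5.3.3, and add a listing of ALT or AST elevations that occur together with raised total bilirubin.
- Check the revised panel against the bilirubin row of the grading scale in the Operations Manual, so that whichever fraction the scale grades is actually measured.

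The cost is a small assay charge at each draw, with no extra visit and no expected extra blood. The downside is an occasional benign unconjugated elevation that has to be explained.
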